3.4 Assessment of Outcomes

Follow-up Survey via myCap: The follow-up survey will be completed 48 to 72 hours following discharge to assess study outcomes. This will be done via myCap. myCap is an application that research participants will be asked to download on their phones (application is free and available on iPhone and Android phones). myCap leverages REDCap to capture participant/patient reported outcomes via mobile devices. myCap is HIPPA-compliant and secure. All data collected via myCap converts results into a format compatible with REDCap. The primary outcome of dosing accuracy will be assessed along with secondary outcomes (medication adherence and medication comprehension) via surveys in myCap. Caregivers will also be asked who administered the medication, what kind of teaching they received in the hospital prior to discharged (i.e., did teach-back, show-back occur), whether any serious medication errors occurred with the patient or other children in the home and/or if there were unplanned visits to a health care provider (see included follow-up survey). Caregiver self-efficacy for administering medicines to their children will be assessed using a standardized scale called the Medication Understanding and Use Self-Efficacy Scale (MUSE). See included document for RCT follow-up survey. We anticipate that the caregiver follow-up survey this will take <15 minutes to complete.

Primary Outcome: Dosing accuracy will be the primary outcome and will be assessed through self-report (reported dose) and through observation (observed dose) at follow-up. The primary outcome will be *observed dosing accuracy*. For *observed dosing accuracy*, caregivers will be asked to draw up a dose of their child's medication using the provided oral dosing syringe and send a secure picture of the syringe via myCap to research study staff (see Figure 2 as an example). The primary outcome will be assessed as a continuous percent difference from the prescribed dose (in milliliters). For *reported dose*, caregivers will be asked to report the prescribed volume (in milliliters) of medication to be given with each dose during the follow-up myCap survey. This will be compared to the prescribed dose in the electronic medical record. For both measures, dosing accuracy will also be assessed as a dichotomous outcome and considered accurate if it is within 20% of the prescribed dose similar to prior studies.^{5,15}

Safety Monitoring Plan: If any dosing errors are detected via the myCap picture and/or myCap follow-up survey, the research team will provide additional education about proper medication dosing, refer caregivers to the prescribed dose on the medication bottle and refer the caregiver back to their child's health care provider for further questions.

Secondary Outcomes: Secondary efficacy outcomes will include discharge medication adherence and caregiver medication comprehension assessed during the myCap follow-up survey. Adherence will be calculated based on caregiver report of first and last dose of medication (compared to documentation in electronic medical record) and if there were any missed doses or if the medication was never obtained from the pharmacy. Caregiver medication comprehension will be assessed using survey questions as was done in a previous study.²⁹ We will also assess the kind of medication teaching parents received in the hospital and which aspects of the medication teaching caregivers found the most useful. Caregiver follow-up survey is included in the application. We will also collect process and exploratory outcomes as detailed in Table 3.

Table 3. Outcomes and measures obtained during myCap follow-up survey

Primary Outcome		
Outcome	Measurement definition	How measurement will be obtained
Medication Dose Accuracy	Comprehension: >20% deviation from caregiver reported dose as compared to dose in electronic health record (EHR) Adherence: >20% deviation from observed dose as compared to dose in (EHR)	Reported dose accuracy measured via caregiver self-report during post-discharge video conference call For observed dose, caregivers will be asked to measure out the prescribed volume using a syringe and submit a picture of the syringe via myCap
Secondary Outcomes		
Medication Name	Comprehension: Error in reporting medication name Adherence: N/A	Caregiver self-report during myCap follow-up survey
Medication Indication	Comprehension: Error in reporting indication for medication Adherence: N/A	Caregiver self-report during myCap follow-up survey
Medication Frequency	Comprehension: Any error in reporting frequency for medication Adherence: Any error in reporting frequency for medication	Caregiver self-report during myCap follow-up survey
Medication Duration	Comprehension: Any error in reporting duration for medication Adherence: Parent report of first and last dose of medication compared to prescribed duration	Caregiver self-report during myCap follow-up survey
Medication Side Effects	Comprehension: Unable to report any known side effects of the medication (credit for correctly identifying > 1 known side effect or reporting no known side effects) Adherence: N/A	Caregiver self-report during myCap follow-up survey
Exploratory Outcomes		
Clinical Outcomes	Prevalence and type of major dosing errors Unplanned visits to health care providers due to medication errors	Caregiver self-report during post-discharge video conference call Review of EHR 30 days following discharge to assess for any unplanned health care visits

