3.3 Intervention

Intervention: The design of the medication instruction sheet was guided by previous research, our previous qualitative study (IRB#201452), and work by Yin et al.¹⁵ The medication instruction sheet will include a pictogram of a syringe marked with the correct dose of medication as well as information about the dose frequency, route of administration, length of treatment, storage and most common medication side effects (see example medication instruction sheet). The medication instruction sheets will be customized for each patient based on the discharge medicine, printed and used to facilitate discharge medication counseling which will include demonstration of accurate dosing with a standardized instrument (i.e., dosing syringe) by research staff followed by caregiver “show-back” of how they plan to administer the medication at home and “teach-back” regarding dosing amounts, times and end dates of medications and common side effects. This will be standardized within an intervention script (see included document) and will be piloted prior to implementation. A clear dosing syringe will be provided to the family prior to discharge. The syringe will be the smallest syringe that would allow administration of the appropriate dose. Caregivers will be given the instruction sheet to use at home. If children receive more than one liquid discharge medication, the intervention will be completed for only one randomly selected medication. We anticipate the intervention will take approximately 10 minutes. We anticipate that the eligibility screening, initial survey and intervention will take approximately 25 minutes to complete.

Usual Care: Caregivers in the usual care group will receive standard of care discharge communications per unit routine, including counseling regarding prescribed medications and post-discharge instructions, return precautions, and follow-up appointments by the pediatric nursing staff. At our institution, children discharged with a liquid medication from our outpatient pharmacy are provided with a dosing syringe as part of routine care. All communications about discharge medication instructions will be at the discretion of the clinical team as part of routine care. An additional dosing syringe will be supplied in a sealed envelope to be used at the discharge follow-up visit in order to standardize the assessment of the primary outcome of observed dosing accuracy.

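### The duration part of adherence needs the last dose of the course, but adherence is collected only at 48-72 hours, before that dose is due in any course with 5 or more days remaining at discharge

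*Combined protocol and SAP*

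**What the plan says.** Section 3.4 fixes the time of assessment: "The follow-up survey will be completed 48 to 72 hours following discharge to assess study outcomes". It places adherence in that survey: "Secondary efficacy outcomes will include discharge medication adherence and caregiver medication comprehension assessed during the myCap follow-up survey". The definition in the text is "Adherence will be calculated based on caregiver report of first and last dose of medication (compared to documentation in electronic medical record", together with any missed doses and failure to obtain the medication.

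In the Medication Duration row of Table 3, the adherence entry is "Parent report of first and last dose of medication compared to prescribed duration". The comprehension entry in the same row is "Comprehension: Any error in reporting duration for medication". The source given for the row is the myCap survey.

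Other provisions that bear on the point:

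- Table 2 (section 3.1) requires a course of at least 3 days and sets no maximum.
- The only later data collection in Table 3 is "Review of EHR 30 days following discharge to assess for any unplanned health care visits".
- Section 3.2 has medication frequency and duration extracted from the health record.
- Section 3.3 includes teach-back "regarding dosing amounts, times and end dates of medications and common side effects".
- The survey is a separate document: "See included document for RCT follow-up survey".

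**The concern.** To compare the last dose with the prescribed duration, the last dose must already have been due. The survey closes at 72 hours, and eligible courses may run much longer. For those courses the item cannot show whether treatment was completed, and what it does show depends on how the caregiver understands the question.

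Better adherence is part of the hypothesis in the Specific Aim, and adherence is a named secondary efficacy outcome. Two different harms are possible. If caregivers report the most recent dose, the item largely reflects course length and the hour of the survey. Randomization balances course length on average, and the documents give no reason for survey time to differ by arm, so the main loss is information. If caregivers report the planned stop date, that part records knowledge that the intervention teaches directly. Better recall in the intervention arm could then be reported as better adherence.

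**Working it through.** The plan gives no figure for adherence, so there is none to reproduce. The sample size in section 3.5 concerns dosing error and does not enter.

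**Inputs from the documents.** The survey window is 48-72 h after discharge (section 3.4). Courses last at least 3 days, with no maximum (Table 2).

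**Assumptions.** The documents give no distribution of course length or dose frequency. Let L be the days of treatment remaining at discharge and f the doses per day, 1 to 4. If hospital days count toward the prescription, L is what is left at discharge.

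**Step 1: evenly spaced doses, first home dose at 0 h.** There are L × f doses, 24/f hours apart, so the last falls at 24L - 24/f hours. A later first dose only moves it later.

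| L (days) | f = 1 | f = 2 | f = 3 | f = 4 |
|---|---|---|---|---|
| 3 | 48 h | 60 h | 64 h | 66 h |
| 4 | 72 h | 84 h | 88 h | 90 h |
| 5 | 96 h | 108 h | 112 h | 114 h |
| 7 | 144 h | 156 h | 160 h | 162 h |
| 10 | 216 h | 228 h | 232 h | 234 h |

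**Step 2: calendar days.** Count the discharge day as day 1, with discharge at clock hour d (d < 24). Day L begins 24(L - 1) - d hours after discharge.

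- L = 5: day 5 begins at 96 - d, which exceeds 72 for every d. At the extreme, discharge at midnight with a last dose at 07:00 on day 5 gives 72 + 7 = 79 h. With discharge at 08:00-21:00 and doses at 06:00-22:00 (assumed), the range is 96 + 6 - 21 = 81 h to 96 + 22 - 8 = 110 h.
- L = 4: day 4 runs from 72 - d to 96 - d, so the last dose can fall anywhere from 48 to 96 h. Whether it falls in the window depends on frequency and on how days are counted.

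Five days is therefore the cut-off that holds under both conventions. It is conservative, because many 4-day courses, and some 3-day courses surveyed near 48 h, are unfinished too.

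**Step 3: how much of the course can have been given.** By 72 h at most 3f + 1 evenly spaced doses are due out of L × f. That share is largest at f = 1, where it is 4/L. Calendar counting also allows at most four days' doses. Under full adherence the maximum is 4/5 = 80% for 5 days, 4/7 = 57% for 7 days and 4/10 = 40% for 10 days. At 48 h with f = 4, nine doses are due: 9/20 = 45%, 9/28 = 32% and 9/40 = 23%.

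**Step 4: each meaning of last dose.**

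- *Most recent dose.* By step 3, a child who has missed nothing still falls short of the prescribed duration.
- *Planned stop date.* Nothing about dosing has been observed. That part of the item measures end-date knowledge.
- *Dosing already stopped early.* This can be measured at 48-72 h, but the comparator is the status expected at the survey, not the full duration that Table 3 names.

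**Step 5: another source of completion data.** The 30-day record review is for unplanned visits. Table 3 mentions a video call, but only for reported dose and clinical outcomes, with no later date. No refill check, bottle check or end-of-course contact is described.

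**The case against.** The strongest reply is that the survey form is a separate document and may ask a sensible question. The text of section 3.4 compares with the health record, which is broader than prescribed duration and could allow a check of status at the time of the survey. This stands in part. The form may settle which reading applies, and an early-stopping question would be useful. But Table 3 names the full duration, and no form completed by 72 h can record a dose not yet due. The definition needs correcting either way.

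A reader might infer that, on the stop-date reading, the item merely repeats the comprehension entry in the same row. The documents do not support that in full: the item also uses the first dose, so it still detects a delayed start. Only the end-date part overlaps.

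A reader might also infer that a true difference between arms shrinks by a calculable amount. The plan states no scoring rule, composite or test for adherence, so no such figure can be derived.

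It is also fair to say that the scope is small: one component of one secondary outcome.

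**Conclusion.** The concern holds for the duration component. Completion cannot be observed for any course with 5 or more days remaining at discharge. The last dose comes at 96-114 h with one to four evenly spaced doses a day, and after 72 h on any calendar-day count. These times rest on the stated spacing and counting conventions. The share of participants affected is unknown, because the documents give no course lengths. They also do not say whether the 3-day minimum runs from discharge or from the start of treatment.

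A reader might infer that adherence as a whole cannot be measured, or that the trial's main result is in doubt. Neither follows. First dose, missed doses to date, medication never obtained and observed dose can all be assessed at 48-72 h, and the primary outcome and sample size do not use this item. Nor do the documents show bias between arms on the most-recent-dose reading. The risk of a difference by arm belongs to the stop-date reading, through the teach-back. The point should be fixed, but it does not threaten the trial. Confidence is medium, since the survey form has not been seen.

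**What to change.** In section 3.4 and Table 3:

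- Replace the comparison with prescribed duration by adherence from discharge to the survey time stamp: delayed start, any missed dose, medication never obtained, and dosing already stopped before the prescribed end. Use the last element only where the survey records the last dose given.
- Score a reported stop date as comprehension only.
- Label the outcome 'adherence in the first 48-72 hours'.
- Report, pooled over arms, how many courses were unfinished at the survey, using the duration already extracted from the health record.
- Date the change and make it without sight of outcomes by arm.

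This needs wording and one count, with no extra contact. It applies to survey respondents: 200 × 0.70 = 140 to 200 × 0.75 = 150 at the planned 25-30% loss to follow-up. The price is a conclusion limited to early adherence, and a secondary outcome redefined late, since the document's revision date of 4/21/2022 falls well into the anticipated 12 months of enrollment from July 1, 2021. A contact at the end of the course would keep completion as an outcome. It would add a contact for every family, and it would mainly serve participants enrolled after the change.

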Specific Aim *In a randomized controlled trial, we will test the efficacy of a health literacy-informed communication intervention on caregiver discharge medication dosing accuracy, adherence, and comprehension. We hypothesize that a useable, health literacy-informed medication counseling intervention will be efficacious in reducing liquid medication dosing errors and improve adherence and medication comprehension among caregivers following hospital discharge for children receiving liquid medication as compared to usual care.*

The primary outcome is observed dosing accuracy assessed via picture of an oral dosing syringe submitted by a caregiver 48-72 hours following discharge and compared to the prescribed dose in the chart. The primary outcome will be a continuous measure of percent difference of the caregiver submitted photo compared to the prescribed dose (in mL). The primary measure will also be assessed as a dichotomous variable as +/- 20% from the prescribed dose. Secondary outcomes include caregiver medication adherence and medication comprehension assessed via caregiver follow-up survey.

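### In Table 3 the adherence definition for medication frequency repeats the comprehension definition, and the table's adherence components differ from those in the Secondary Outcomes paragraph

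*Combined protocol and SAP*

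**What the plan says.** Section 2.0 (Specific Aim) names two secondary constructs: "Secondary outcomes include caregiver medication adherence and medication comprehension assessed via caregiver follow-up survey". Section 3.4 repeats the pairing and calls both efficacy outcomes: "Secondary efficacy outcomes will include discharge medication adherence and caregiver medication comprehension assessed during the myCap follow-up survey".

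Adherence is then defined in two places in section 3.4.

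- **Secondary Outcomes paragraph.** "Adherence will be calculated based on caregiver report of first and last dose of medication (compared to documentation in electronic medical record"), together with "if there were any missed doses or if the medication was never obtained from the pharmacy".
- **Table 3.** The Medication Frequency row reads "Comprehension: Any error in reporting frequency for medication Adherence: Any error in reporting frequency for medication". The Medication Duration row has "Adherence: Parent report of first and last dose of medication compared to prescribed duration". The Medication Dose Accuracy row, listed under the primary outcome, has "Adherence: >20% deviation from observed dose as compared to dose in (EHR"). For name, indication and side effects, adherence is marked as not applicable.

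Section 3.3 says that the intervention sheet states the dose frequency, that teach-back covers dosing times, and that the caregiver takes the sheet home. Usual care counselling is left to the clinical team.

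**The concern.** Adherence concerns what was given, and comprehension concerns what is understood. When one row uses a single definition for both, a caregiver who correctly states twice daily but gives the medicine once daily has no frequency adherence error. A caregiver who misstates the frequency but follows the written schedule does have one.

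This matters more here than in a trial of a drug, because the intervention acts directly on knowledge of the frequency. Caregivers in that arm can answer a frequency question from the teach-back or from the sheet in front of them. A between-arm difference on this item could therefore be read as a change in behaviour when only knowledge has changed.

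The second problem is that the paragraph and the table list different components for the same outcome. Section 3.5 describes no analysis of adherence and no rule for combining items, so nothing there settles which list applies. An analyst could follow either, including after seeing the data.

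**Working it through.** The plan states no figure for adherence or frequency, so the check is mainly a comparison of wording.

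**1. Rows of Table 3 where adherence applies**

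| Row | Comprehension | Adherence | Distinct? |
|---|---|---|---|
| Dose | Reported dose more than 20% off the record | Photographed dose more than 20% off the record | Yes |
| Frequency | Any error in the reported frequency | Any error in the reported frequency | No |
| Duration | Any error in the reported duration | First and last dose against prescribed duration | Yes |

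Two of the three rows separate the constructs. Only frequency does not.

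**2. What the frequency row can detect**

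In arm *a*, let k(a) be the proportion who misreport the frequency and m(a) the proportion who do not give the medicine at that frequency. Followed literally, the row gives:

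- comprehension error = k(a)
- adherence error = k(a)
- between-arm difference on either = k(control) − k(intervention)

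The quantity m(a) does not appear. If teaching lowers k and leaves m unchanged, the adherence item still shows k(control) − k(intervention). This assumes that one survey answer feeds both scores, which is what the table's wording implies.

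**3. Illustration**

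Take a medicine prescribed twice daily, given once daily, with the frequency correctly reported as twice daily. The survey is at 48 to 72 hours.

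- Doses due by 48 hours: 2 × 2 = 4; given: 1 × 2 = 2.
- Doses due by 72 hours: 2 × 3 = 6; given: 1 × 3 = 3.
- Frequency adherence item in Table 3: no error.
- Secondary Outcomes paragraph: missed doses, so the shortfall counts.

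The same caregiver is classified differently by the two parts of section 3.4.

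**4. Components side by side**

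| Component | Paragraph | Table 3 |
|---|---|---|
| First and last dose | Yes | Yes (duration row) |
| Missed doses | Yes | No |
| Medicine never obtained | Yes | No |
| Frequency | No | Yes (same as comprehension) |

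Only first and last dose appears in both. The photographed dose carries an adherence label in Table 3 but sits under the primary outcome, so it is not counted as a mismatch here.

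**5. Sample size**

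The only planning figure is for dosing error: 30% against 10%, 80% power, two-sided alpha 0.05. The uncorrected formula is n₀ = [1.96·√(2·0.2·0.8) + 0.842·√(0.3·0.7 + 0.1·0.9)]² / 0.2² ≈ 61.6, that is 62 per arm. With continuity correction, n = (n₀/4)·[1 + √(1 + 4/(n₀·0.2))]² ≈ 71.3, that is 72 per arm, as the plan states. For loss to follow-up, 144/0.75 = 192 and 144/0.70 ≈ 206, so the planned 200 lies between. No adherence definition enters this calculation.

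**The case against.** The strongest reply is that a reader might infer from the frequency row that the whole adherence objective is scored on knowledge. The documents do not support that. The paragraph calculates adherence from first and last dose, missed doses and medicine never obtained, all of which concern what was done. The duration row also uses first and last dose, and the dose row uses a photographed draw. The once-daily caregiver above would be caught by the missed-dose component. Nothing gives the table precedence over the paragraph. This stands, and it limits the point to one item and a mismatch.

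A reader might also infer that the two frequency scores must agree in every participant. The follow-up survey is cited as an included document but is not in the supplied text. It may ask separately what was prescribed and what is being given, and the authors may have meant the frequency actually given. Full agreement therefore follows from the table's wording only. The reply does not rescue that wording, which gives both constructs the same definition and source.

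A third inference is that Table 3 contains nothing on doses given, or that the trial could claim better adherence on this item alone. The first overlooks the duration row, and the three not-applicable rows have no adherence counterpart to omit. The second needs a rule for combining items, and none is stated.

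**Conclusion.** Wrong as written, limited to one item of a secondary outcome. Followed literally, the frequency adherence item measures knowledge, which the intervention directly teaches, and any arm difference on it would be the comprehension difference under another name. Separately, Table 3 and the Secondary Outcomes paragraph give different component lists: two of the paragraph's components are missing from the table, and one of the table's is missing from the paragraph.

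This rests on the table's wording as supplied, and the survey questions could not be checked. It does not extend to the adherence objective as a whole, to the primary outcome of observed dosing accuracy, or to the sample size. The size of any bias on the item cannot be estimated, because the plan gives no expected frequency-error or missed-dose rates.

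**What to change.** Three edits to section 3.4:

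1. In the Medication Frequency row, keep misreported frequency under comprehension only.
2. Define frequency adherence in that row by caregiver-reported doses given or missed since discharge, compared with the doses prescribed for that period. This uses the missed-dose information that the section already names.
3. Make the adherence components in Table 3 the same as those in the Secondary Outcomes paragraph, by adding missed doses and medicine never obtained to the table and naming the revised frequency item in the paragraph. While doing so, state how the components combine into the adherence outcome.

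The cost is a wording change and possibly one survey question, if the survey does not already ask how many doses were given or missed. No extra visit or staff is needed. The downside is that caregivers recall dose counts imperfectly, although the recall period is only 48 to 72 hours.
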